1.3. Schedule of Activities

A consolidated Schedule of Activities for the Master protocol PLATFORMPACRD2001 and this ISA is presented in [Table 1](#).

Table 1: Consolidated Schedule of Activities - PLATFORMPACRD2001 and 67864238PACRD2001										
67864238PACRD2001 specific events	Period	Screening ^a	Treatment Phase ^b				Early Termination ^c	Final Safety Follow-up ^d		
			Week	-5 weeks	0	2	4	8	12	
Study Procedures										
Screening/Administrative										
Informed consent ^e		X								
Master protocol inclusion/exclusion criteria ^f		X		X						
X JNJ-67864238 inclusion/exclusion criteria ^f		X		X						
Medical history and demographics		X								
Immunization history		X								
Stool studies to evaluate for enteric pathogens ^g				X						
Height		X								
X^v QuantiFERON-TB test		X								
X^w Chest radiograph		X								
HIV, HBV and HCV testing		X								
Follicle stimulating hormone test (optional at the discretion of the investigator)				X						
Serum pregnancy test ^h		X								
X (Week 4 only) 12-lead ECG		X			X		X	X		
Training on diary completion		X								
Randomization				X						
Study Intervention Administration										
X Dispense study intervention				X	X	X	X			
X Administer study intervention				Daily Self-Administration						
X Study intervention accountability				X	X	X	X	X		
Safety Assessments										
Physical examination		X				X	X	X		

Table 1: Consolidated Schedule of Activities - PLATFORMPACRD2001 and 67864238PACRD2001									
67864238PACRD2001 specific events	Period	Screening ^a	Treatment Phase ^b					Early Termination ^c	Final Safety Follow-up ^d
			Week	-5 weeks	0	2	4	8	12
Study Procedures									
Body weight		X		X	X	X	X	X	X
Vital signs ⁱ		X		X	X	X	X	X	X
Urine pregnancy test ^j				X	X	X	X	X	X
Concomitant therapy review		X		X	X	X	X	X	X
Adverse events review		X		X	X	X	X	X	X
X^x Tuberculosis evaluation/other infection assessment		X		X	X	X	X	X	X
Efficacy Assessments									
Collect and review diary entries ^k				X	X	X	X	X	X
X^{bb, cc} CDAI assessments ^{l, m}		X		X	X	X	X	X	X
Fistula exam				X	X	X	X	X	X
Abdominal pain NRS assessment ⁿ				X	X	X	X	X	X
Stool sample (fecal lactoferrin and calprotectin) ^o		X		X	X	X	X	X	X
X^y Video ileocolonoscopy with biopsies for RNA and histology ^p		X						X	X
PROMIS-29 ^q				X				X	X
PGIC								X	X
PGIS				X				X	X
Clinical Laboratory Assessments									
Hematology ^{r, s}		X		X	X	X	X	X	X
Chemistry ^{r, s}		X		X	X	X	X	X	X
CRP		X		X	X	X	X	X	X
Pharmacokinetics/Immunogenicity									

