- q. The PROMIS surveys should be administered before any clinical procedures or tests are performed. PROMIS surveys will only be collected in countries where translations are available.
- r. Hematology and chemistry tests at Week 0 are not required if screening laboratory tests were performed within 2 weeks before the Week 0 visit.
- s. Blood samples should be collected after PROs are administered and vital signs collected. All reasonable attempts should be made to collect samples at the scheduled timepoints and record the actual times of sample collections.
- t. All reasonable attempts should be made to collect samples at the scheduled timepoints and record the actual dates and times of sample collections.
- u. Requires completion of a separate informed consent.

67864238PACRD2001 specific

- v. All participants will undergo QuantiFERON-TB testing. In countries where the QuantiFERON-TB test is not registered/approved, TB skin testing will also be required (recommended but not required for study centers in Ukraine if tuberculin is not available).
- w. Chest radiograph (posterior-anterior view) must be obtained within 3 months before the Week 0 visit.
- x. If TB is suspected at any time, a chest radiograph and QuantiFERON-TB test should be performed. In countries where the QuantiFERON-TB test is not registered/approved, TB skin testing should also be performed (recommended but not required for study centers in Ukraine if tuberculin is not available).
- y. Biopsy samples will also be used for the measurement of JNJ-67864238 tissue concentration.
- z. Venous blood samples of sufficient volume for the measurement of JNJ-67864238 plasma concentrations and to assess serum antibodies to JNJ-67864238 will be collected from all randomized participants as follows:
 - Before study intervention administration (ie, predose) at Week 0, Week 2, Week 4, Week 8, and Week 12
 - i. The Weeks 2 and 8 sample should be of sufficient volume to assess the plasma concentration of JNJ-67864238 (and a backup sample).
 - ii. The Weeks 0, 4, and 12 samples should be of sufficient volume to assess the plasma concentration of JNJ-67864238 (and a backup sample) and to assess serum antibodies to JNJ-67864238.
 - After study intervention administration (ie, postdose) at Week 12 within 2 to 4 hours
 - At the early termination visit (if applicable)
- aa. A single stool sample (ie, bowel movement) will be collected at each visit to assess JNJ-67864238 stool concentration and biomarkers.

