**Table 1. Visit Windows**

Scheduled Study Day	Visit Window
Screening	-999, -1
Week 0 Day 1*	1, 7
Week 2 Day 1 (Day 15)	8, 21
Week 4 Day 1 (Day 29)	22, 42
Week 8 (Day 57)	43, 70
Week 12 (Day 85)	71, 98
Safety Follow-up (Week 16)	99, 999
* Study Day 1 begins on the day of randomization. Each Week consists of 7 days.	

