#### 5.7.1.1. PTG-200 Concentrations

Blood, colonic tissue and fecal samples for determining PTG-200 concentrations will be collected from all participants according to the schedule in the Protocol Schedule of Activities. Plasma, colonic tissue and fecal PTG-200 concentrations will be used to evaluate local and systemic drug exposure.

Plasma, colonic tissue and fecal PTG-200 concentrations will be summarized using descriptive statistics (i.e., n, arithmetic mean, standard deviation [SD], coefficient of variation [%CV], median, range [minimum and maximum], and interquartile [IQ] range) at each visit. PK data may be displayed graphically.

The following analyses will be performed as appropriate.

- Summary of plasma PTG-200 concentration over time
- Proportion of participants with plasma PTG-200 concentration below the lowest quantifiable concentration in a sample at each visit
- Summary of plasma PTG-200 concentrations over time by baseline body weight (quartiles). Other covariates may also be applied.
- Plots of median plasma PTG-200 concentrations over time

- Plots of median plasma PTG-200 concentrations over time by baseline body weight ( $\leq$ median,  $>$ median).

As applicable, a similar approach as described above for plasma PTG-200 concentration will also be applied to colonic tissue and fecal PTG-200 concentrations.

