### 5.7.1.2. Data Handling Rules

Unless otherwise specified, the following data handling rules will apply to PK sample analyses:

- Plasma concentration summaries will be based on the actual treatment received.
- All plasma, colonic tissue and fecal concentration summaries for a particular timepoint will include data obtained from treated participants at the timepoint of interest without imputing any missing data.
- A concentration not quantifiable (below the lower limit of quantification) will be treated as 0 in the summary statistics and shown as the lower limit of quantification ( $<$  LLOQ) in the data listings.
- The data from a participant who meets 1 of the following dosing deviation criteria will be excluded from the by-visit data analyses from that point onwards:
  - Discontinued study agent administrations
  - Skipped an administration
  - Received an incomplete/ incorrect dose
  - Received an incorrect study agent
  - Received an additional dose
  - Received an administration outside the dosing window specified in [Table](#) .

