**Table 4: Dosing Window**

Visit	Window
Week 0 through Week 12	$\pm$ 5 days from scheduled visit day
Final Safety and Efficacy Follow-up visits	$\pm$ 14 days from scheduled visit day

All participants and samples excluded from the analysis will be clearly documented in the Clinical Study Report.

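### The PK dosing window of ±5 days around visits does not fit a drug taken daily at home, and no SAP rule compares sample time with dose time

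*SAP*

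**What the plan says.** SAP 5.7.1.2 lists dosing deviations that affect the PK summaries. A participant who meets any one of them "will be excluded from the by-visit data analyses from that point onwards". One of them applies when the participant "Received an administration outside the dosing window specified in" Table 4. Another is a single skipped administration.

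Table 4 has two rows. For Week 0 through Week 12 the window is ± "5 days from scheduled visit day". For the "Final Safety and Efficacy Follow-up visits" it is ±14 days.

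The protocol's Schedule of Activities (1.3) describes dosing as "Daily Self-Administration", and protocol 6.1 provides for storage at home. Plasma is sampled before dosing at Weeks 0, 2, 4, 8 and 12 (1.3 footnote z; 8.5.1). There is one further sample: "After study intervention administration (ie, postdose) at Week 12 within 2 to 4 hours".

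SAP 5.7.1.1 summarises concentrations at each visit and includes "Plots of median plasma PTG-200 concentrations over time". SAP 5.7.1.3 may relate concentration quartiles to CDAI outcomes at Week 8 or Week 12.

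Protocol 9.4.5 has its own, more general PK exclusion. It leaves participants out of the descriptive statistics when their data do not permit an accurate reading of the concentrations, and it gives missing dose and sample times as one example.

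**The concern.** A window around scheduled visits suits a drug given at those visits. Here most doses are taken between visits, which are up to 28 days apart, so a visit-based window either condemns ordinary dosing or tests nothing useful. The follow-up row shows the same mismatch: the safety follow-up is four weeks after the last dose (protocol 1.3, footnote d), so there is no administration for a ±14-day window to judge.

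The timing distinction the protocol does draw is in hours: before the dose, or 2-4 hours after it. None of the SAP 5.7.1.2 criteria compares sample time with dose time. Two plasma samples with different meanings also share the Week 12 visit, while the summaries are organised by visit.

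PK is part of a secondary objective (SAP 1.1), and low systemic exposure is central to the drug's rationale (protocol 2.3). The plasma summaries should therefore follow a rule that can be applied as written.

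**Working it through.** The plan gives no figure of its own to reproduce. The check is a count of days under each reading of Table 4.

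**Inputs**
- Scheduled visit days: 1, 15, 29, 57, 85 (SAP Table 1).
- Window: ±5 days (SAP Table 4).
- Dosing: daily (protocol 1.3). The number of doses per day is redacted, and the count does not depend on it. The first dose is taken to be on Day 1.
- Protocol visit window: ±4 days (protocol 1.3, footnote b).

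**Reading 1: the window applies to every administration.** A day is in-window if |day − visit day| ≤ 5 for at least one visit.

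| Visit day | In-window days (Days 1-85) | Count |
|---|---|---|
| 1 | 1-6 | 6 |
| 15 | 10-20 | 11 |
| 29 | 24-34 | 11 |
| 57 | 52-62 | 11 |
| 85 | 80-85 | 6 |
| Total | | 45 |

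Out-of-window days are 7-9 (3), 21-23 (3), 35-51 (17) and 63-79 (17): 3 + 3 + 17 + 17 = 40, and 40/85 = 47%. The first is Day 7. The Week 2 visit can come no earlier than Day 15 − 4 = Day 11, so the breach precedes the first post-baseline PK sample. A participant who did not dose on Day 7 would meet the skipped-dose or discontinuation criterion instead.

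The first failing day is sensitive to the width: ±4 days fails first on Day 6, ±7 days on Day 37, and ±14 days never.

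**Reading 2: the window applies only to the dose linked to a visit.** A visit held within the protocol's ±4 days always satisfies ±5. No participant on schedule is excluded.

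**Reading 3: Week 0 through Week 12 is one continuous span.** It runs from five days before Day 1 to Day 85 + 5 = Day 90. No on-treatment dose falls outside it.

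**What no reading can detect.** A predose sample drawn on the visit day, an hour or more after that day's dose at home, involves an administration zero days from the visit. A Week 12 postdose sample at, say, 6 hours looks the same to a rule that counts days. The data for a proper check already exist: dose date and time are captured (protocol 6.1), and exact PK sampling times are recorded (protocol 8.5.1).

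**The neighbouring skipped-dose criterion.** One skipped administration also removes the participant from then on. The documents give no adherence rate. Assuming independent daily adherence p, the chance of no skipped day before the Day 85 visit is p^84:
- p = 0.99: 43%, or 54 × 0.430 = 23.2 of the 54 planned active participants
- p = 0.98: 18%, or 54 × 0.183 = 9.9
- p = 0.95: 1%, or 54 × 0.013 = 0.7

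These figures are illustrative. They show that removing the window alone would leave a permanent exclusion that is severe for a daily drug.

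**The case against.** The strongest reply is that no analyst would apply Table 4 to each home dose. The table is indexed by visit and sits in a rule about by-visit analyses. On the two softer readings it is nearly inert, and a literal application would show up at once as empty tables. This stands as far as it goes. A reader might infer from the Day 7 result that none of the 54 active participants will contribute post-baseline PK data; that follows only from the least plausible reading. Even then the exclusion covers the by-visit analyses only: protocol 9.4.5 still lists the available concentrations for all participants, and the PK-efficacy work in SAP 5.7.1.3 is optional and not expressly by-visit.

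A reader might also infer that the Week 12 predose and postdose samples will be pooled and show a false rise. The documents do not say so. The protocol labels the two samples separately, SAP 5.7.1.2 also speaks of timepoints, and table layouts are left to a separate specification (SAP 1). Pooling is possible, and its size cannot be calculated from the documents.

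Nor do the documents establish that plasma level depends on hours since dosing at the trial dose. The Phase 1 statement on accumulation (protocol 2.2) is limited to dose levels up to a redacted group.

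Finally, protocol 9.4.5's general exclusion could be used against a mistimed sample. That is a fair point, but the SAP's list omits it, the omission is not recorded among the changes in SAP Appendix 2, and neither document gives an explicit dose-to-sample rule.

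What remains is that the rule as written excludes everyone or almost no one, depending on a reading the SAP leaves open, and that it has no bearing on the timing distinction the protocol makes.

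**Conclusion.** The concern holds in limited form. Table 4 and its criterion are wrong for a drug self-administered daily. Literally, 40 of 85 days (47%) breach the window and an adherent participant leaves the by-visit PK summaries from Day 7; on the softer readings the criterion does almost nothing. In no case can it identify a mistimed predose sample or a Week 12 postdose sample outside 2-4 hours. How the two Week 12 plasma samples are separated is not stated.

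The day count rests on the scheduled days in SAP Table 1 and on dosing from Day 1. Which reading the sponsor would use is not known, nor is the frequency of mistimed samples. It would go too far to conclude that the PK data will be lost, or that the exposure evidence is unreliable.

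The consequences are confined to descriptive PK and exploratory PK-efficacy summaries. Sampling is sparse and no PK parameters are to be estimated (protocol 8.5.3). The primary CDAI analysis and the decision rules do not use these data. It is worth correcting before the PK summaries are programmed.

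**What to change.** In SAP 5.7.1 and Table 4:

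1. Delete the dosing-window criterion and Table 4.
2. Classify each plasma sample from recorded clock times: predose only if drawn before that day's dose; Week 12 postdose only if drawn 2-4 hours after the recorded dose. List mistimed samples but leave them out of the summaries.
3. Summarise and plot Week 12 predose and postdose as separate nominal times, and state which one enters the PK-efficacy quartiles in 5.7.1.3.
4. Apply the remaining dosing-deviation criteria, including the skipped-dose one, to the samples they affect (plasma, fecal or tissue) rather than to the participant permanently.
5. Align the list with the accuracy exclusion in protocol 9.4.5.

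This changes SAP wording only. Dosing, visits and data collection stay as they are, because dose and sample times are already required. The cost is minor extra programming and the loss of a few mistimed samples from the summaries.

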**Table 4: Dosing Window**

Visit	Window
Week 0 through Week 12	$\pm$ 5 days from scheduled visit day
Final Safety and Efficacy Follow-up visits	$\pm$ 14 days from scheduled visit day

All participants and samples excluded from the analysis will be clearly documented in the Clinical Study Report.

### 5.7.1.3. PK vs Efficacy

To explore the relationship between PTG-200 plasma, colonic tissue or fecal concentrations and efficacy endpoints, the following analyses may be explored:

- The relationship between PTG-200 plasma, colonic tissue or fecal concentrations (quartiles) and change from baseline in CDAI score, clinical response and clinical remission status at

Week 8 or Week 12 may be explored. Summaries by Bio-IR status (yes or no) (i.e., Bio-IR and Bio-NF) and by SNP status (positive or negative) may also be provided.

## **5.7.2. Immunogenicity**

### **5.7.2.1. Antibodies to PTG-200**

Immune response analyses will be based on the Immunogenicity Analysis Set.

The antibody to PTG-200 status (positive at any time, negative) and titers will be summarized by treatment group for participants who receive a dose of PTG-200 and have appropriate samples for detection of antibodies to PTG-200 (ie, participants with at least 1 sample obtained after their first dose of PTG-200). The maximum titers of antibodies to PTG-200 will be provided for participants who are positive for antibodies to PTG-200.

A listing of participants who are positive for antibodies to PTG-200 will be provided. The sample antibody status, the titer, and the neutralizing antibody status to PTG-200 will be listed by visit. This listing will also provide information regarding dose administered, PTG-200 plasma concentration, and CDAI for all applicable visits. In addition, a list of antibody to PTG-200 status in participants who discontinued study agent early will be provided.

### **5.7.2.2. Neutralized Antibodies to PTG-200**

The incidence of neutralizing antibodies (NAbs) to PTG-200 will be summarized for participants who are positive for antibodies to PTG-200 and have samples evaluable for NAbs to PTG-200.

### **5.7.2.3. Antibody vs Efficacy/PK**

Plasma PTG-200 concentrations, clinical remission/response status, and change from baseline in the CDAI score over time may be summarized by antibody to PTG-200 status if sufficient numbers of participants are positive for antibodies. Plots of median plasma PTG-200 concentrations over time by antibody to PTG-200 status may also be provided. The evaluation between colonic tissue PTG-200 concentration and the identified efficacy parameters will be performed as appropriate.

## **5.7.3. Pharmacogenomic**

A whole blood sample collection for SNPs and DNA analysis will be collected from all participants at Screening who have signed an optional pharmacogenomics consent form. DNA testing will be done to search for links of specific genes to disease or response to JNJ-67864238 drug. Exploratory genetic analyses on DNA collection from participants who signed the optional DNA consent will be presented in a separate technical report.

## **5.7.4. Pharmacokinetic/Pharmacodynamic Relationships**

The relationship between plasma concentration of PTG-200 and PD may be analyzed graphically. Similarly, the relationship between colonic tissue or fecal PTG-200 concentration and PD endpoints listed above may be analyzed graphically. If any visual trend is observed, a suitable PK/PD model may be developed to describe the exposure-response relationship. In the latter case, the results of the PK/PD modeling analysis will be presented in a separate technical report.

### **5.7.5. Biomarker Analyses**

Biomarker assessments will be conducted to examine the biological response to treatment and to identify biomarkers that are relevant to PTG-200 treatment and/or Crohn's disease. Assessments include the evaluation of relevant biomarkers in serum, whole blood (for RNA analysis), stool, and mucosal biopsy samples (for protein, RNA and histology analysis) collected according to the Schedule of Activities in the protocol.

Biomarker analyses will characterize the effects of PTG-200 on the measured biomarkers to identify biomarkers relevant to treatment and to determine if these biomarkers can predict response to PTG-200. Results will be reported in separate technical reports.

### **5.7.6. Health Economics**

#### **5.7.6.1. PROMIS 29**

The PROMIS-29 profile instrument is intended for adults (ages 18 years and older). It is a collection of short forms containing 4 items for each of 7 PROMIS domains: Depression, Anxiety, Physical Function, Pain Interference, Fatigue, Sleep Disturbance, and Ability to Participate in Social Roles and Activities. The PROMIS-29 instrument also includes a Pain Intensity 0-10 NRS in addition to the 7 domains. PROMIS-29 is a universal rather than disease-specific instrument. It assesses all domains over the past 7 days, except for the Physical Function domain, which has no specified timeframe. The raw score of each domain is converted into a standardized score with a mean of 50 and a standard deviation (SD) of 10 (T-Score). The standardized T-score is reported as the final score for each participant. Pain Intensity is presented as raw responses (0-10). For the PROMIS domains of Depression, Anxiety, Physical Function, Pain Interference, and Fatigue, a score of 50 is the mean for the United States general population with an SD of 10 (validated with a large sample of the general US population). Since the other 2 domains (Ability to Participate in Social Roles and Activities and Sleep Disturbance) were not validated with a national sample, a score of 50 represents the mean of the calibration sample (which was enriched for chronic illness so a score of 50 represents a sicker population). A higher PROMIS T-score represents more of the domain being measured. For negatively-worded domains like Anxiety, a T-score of 60 is 1 SD worse than average. By comparison, an Anxiety T-score of 40 is 1 SD better than average. However, for positively-worded domains like Physical Function, a T-score of 60 is better than average.

PROMIS surveys will only be collected in countries where translations are available.

#### **5.7.6.2. Analysis Method**

The analysis will be performed at Week 12. The analysis will include descriptively summarizing change from baseline in PROMIS-29 score. Using MMRM model in comparing treatment difference by LS Mean (SD), LS mean (90% CI). p-Value was based on comparison with placebo model. And other statistical analysis as appropriate.

### **5.7.7. Other Variables and/or Parameters**

Not applicable.

### 5.7.8. Definition of Subgroups

Subgroups of interest in this study include but not limited to:

1. Population
  - a. BIO-IR vs BIO-NF
2. Demographics at baseline:
  - a. Age ( $\leq$  median age,  $>$ median age)
  - b. Sex (male, female)
  - c. Race (White, non-White)
  - d. Weight at baseline ( $\leq$  median,  $>$  median;  $\leq$  1st quartile,  $>$ 1st quartile and  $\leq$  2nd quartile,  $>$ 2nd quartile and  $\leq$  3rd quartile,  $>$ 3rd quartile)
  - e. Center location (North America, Rest of World)
3. Disease characteristics at baseline:
  - a. Crohn's disease duration ( $\leq$  5 years,  $>$  5 years to  $\leq$  15 years, or  $>$  15 years)
  - b. Involved gastrointestinal areas (ileum only, colon only, ileum & colon)
  - c. CDAI score ( $<$ 300,  $\geq$ 300 )
  - d. CRP ( $\leq$  3 mg/L,  $>$  3 mg/L)
  - e. Fecal Calprotectin ( $\leq$ 250  $\mu$ g/g,  $>$  250  $\mu$ g/g)
4. Concomitant Crohn's-disease medication at baseline:
  - a. Oral corticosteroids (including budesonide and beclomethasone dipropionate) (receiving, not receiving)
  - b. Oral 5-ASA compounds (receiving, not receiving)
  - c. Immunomodulators (6-MP/AZA/MTX) (receiving, not receiving)
  - d. Oral corticosteroids (including budesonide and beclomethasone dipropionate) and Immunomodulators (receiving, not receiving)
5. Other:
  - a. Current fistula at baseline (yes, no)

